One of the critical areas where these enzymes show promise is in the modulation of lactate metabolism. Lactate, often produced in higher quantities during intense physical activity, can lead to fatigue and decreased muscle efficiency. The traditional view of lactate as merely a byproduct of anaerobic metabolism has evolved, with current research acknowledging its role as a valuable energy source during prolonged exercise [23]. This shift in understanding opens up new avenues for utilizing enzyme supplementation to optimize lactate utilization. Enzymes such as bromelain and papain, found in pineapples and papayas respectively, have been studied for their potential in improving lactate metabolism. These enzymes are known to facilitate faster clearance of lactate from the bloodstream, thereby enhancing recovery and reducing fatigue [26, 28]. Furthermore, the antioxidant properties of these enzymes play a crucial role in combating oxidative stress, which is often elevated during intense exercise regimes [24, 25]. This reduction in oxidative stress is not only beneficial for immediate recovery but also contributes to long-term muscle health and function. Moreover, the anti-inflammatory actions of these natural enzymes can mitigate the inflammatory response often triggered by high-intensity exercise [27]. By reducing inflammation, these enzymes may enhance muscle recovery and function, thus allowing for more efficient and prolonged exercise performance. This aspect is particularly relevant in training regimens where recovery is as crucial as the exercise itself.

The primary aim of this feasibility study is to examine the effects of fruit and vegetable enzyme supplementation on aerobic capacity and blood lactate response in elderly individuals engaged in HIIE through an exergaming framework. This study is dual-faceted, focusing firstly on the physiological responses and feasibility of an exergaming-HIIE regimen tailored for the elderly, and secondly, on the impact of enzyme supplementation on enhancing these exercise outcomes.

Methods

Participants And Experimental Design

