All participants reported a regular exercise habit (3 times per week within the past year). They also completed the Physical Activity Readiness Questionnaire and confirmed no history of upper limb skeletal muscle injury or major injury. Participants were instructed to avoid strenuous activities and the intake of caffeine or muscle-enhancing supplements for 24 hours prior to the experiment. Before the study commenced, all participants provided personal information, completed health questionnaires, disclosed personal medical history, and signed informed consent forms.

The 16 participants underwent the Exergaming HIIE test as an initial assessment (pre-test). Participants engaged in a 5-minute warm-up on a stationary bike, followed by HIIE using the Nintendo Switch Ring Fit Adventure design. The training method was adapted from the research of [8, 9] and consisted of 8 sets of 20 seconds of

maximum effort exercise with 30 seconds of complete rest between each set, resulting in a total exercise time of 370 seconds. The HIEE design incorporated training modes targeting the deltoid, pectoralis major, latissimus dorsi, and quadriceps muscles in the Nintendo Switch Ring Fit Adventure. Blood lactate levels, heart rate, and ratings of perceived exertion were recorded before, during, and after exercise, and training load was quantified using TRIMP. Participants were matched and divided into two groups, the enzyme group, and the placebo group, based on their blood lactate levels during HIEE. Each group comprised 8 individuals. Supplementation with vegetable and fruit enzymes or maltodextrin commenced three days after the pre-test and lasted for a total of 14 days. On the 14th day, following the completion of supplementation, the participants underwent the Exergaming HIEE test as a post-test.

Ethical Considerations

The human research ethics committee of the local university approved this study, which was also approved by the human research ethics committee of the National Cheng Kung University, Taiwan. (Approval No. NCKU HREC-E-112-419-2). Users volunteered for this study and agreed to participate by signing an informed consent form.

Supplementation Protocol

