muscle groups and provides engaging gaming challenges. The exercise protocol included eight sets of 20-second high-effort exercises, interspersed with 30-second rest intervals, totaling 370 seconds of active exercise time. Specifically, the fitness game mode used was the Adventure Mode in 'Ring Fit Adventure,' comprising exercises targeting the pectoralis major, latissimus dorsi, deltoids, and quadriceps muscles (Figures 2).

[figure not shown]

Figure 2. Experimental flowchart. Ex-: bout of HIIE test; Post-5 min: after 5 minutes of HIIE test; Post-10 min: after 10 minutes of HIIE test. Asterisk (*) indicates lactate test. Asterisk (#) indicates test heart rate and RPE.

Blood Lactate Test

The blood lactate was measured at five time points: before exercise, after the fourth and eighth bouts of exercise, and at 5 and 10 minutes after exercise. The blood lactate were analyzed using a Biosen Cline blood analysis system (EKF-diagnostic, Germany). Capillary blood samples of 10 μ L were collected and added to red blood cell lysis reagent and stored at low temperature until analyzed. Prior to analysis, instrument standardization and test calibration were performed, and the coefficient of variation was determined to be $\leq 1.5\%$. The detection range for blood lactate was 0.5-40 mM [31].

Training Impulse

In this study, the exercise load was represented by the TRIMP [32], which is calculated as the product of exercise intensity and duration. To accommodate the convenience of the experiment, two different TRIMP calculation methods were used, including % HRmax (objective) and RPE (subjective). At the end of each exercise bout (8 bouts in total) and during the recovery period before the next bout (7 bouts in total), participants were asked to report their RPE, and their heart rate was recorded. This process was repeated 8 times.

% HRmax Calculation Method

During the entire HIIE, the participant's HR was recorded every 5 seconds using a heart rate monitor (iHeart Polar, Taiwan) to calculate % HRmax. The block TRIMP

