method developed by S. Edwards [33] was used, which divides the exercise intensity into 5 blocks with corresponding weighting factors (Table 1). The weighted score of each block was multiplied by the exercise time (min) and then summed to obtain the exercise load (arbitrary unit [AU]). The calculation formula is as follows: Exercise load = (Z1 exercise time × 1) + (Z2 exercise time × 2) + (Z3 exercise time × 3) + (Z4 exercise time × 4) + (Z5 exercise time × 5)

Table 1 The Edwards' block TRIMP calculation method

Zone	Intensity	Weighted score
Z1	50%-60% HRmax	1
Z2	60%-70% HRmax	2
Z3	70%-80% HRmax	3
Z4	80%-90% HRmax	4
Z5	90%-100% HRmax	5

RPE Calculation Method

The TRIMP calculation method of Foster, Hector [34] and Foster, Florhaug [35] was used to calculate the exercise load by multiplying the RPE value of each exercise segment by the exercise time and summing them up. The RPE scale used in this method was the CR-10 version modified by Foster, Florhaug [35] based on Borg, Ljunggren and Ceci [36] (Table 2). The calculation formula is as follows: Exercise load (AU) = Borg's CR-10 RPE score × exercise time (min)

Table 2. Borg's CR-10 RPE

0	Rest
1	Very, very easy
2	Easy
3	Moderate
4	Somewhat Hard
5	Hard
6	
7	Very Hard
8	
9	
10	Maximal

Statistical Analysis

All the data were analyzed by SPSS for Windows 20.0. Data are expressed as the mean \pm standard deviation (SD) and 95% confidence interval (95% CI). A mixed design two-way analysis of variance (ANOVA) (group \times time) was used to compare the variables of lactate, heart rate and training impulse between two groups before and after the 14-days of supplementation. Graphs were generated using GraphPad Prism 8.0 (GraphPad Software, San Diego, California, USA). Cohen's conventions for ES (Cohen d) were calculated by the G*Power 3.1 software program (Heinrich-Heine-Universität, Düsseldorf, Germany), where the ESs of 0.2, 0.5, and 0.8 are considered small, medium, and large, respectively. Statistical significance was set as $p < 0.05$.

References

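### Groups were matched on pre-test exercise lactate, but the lactate analysis uses neither the matching nor regression on the pre-test value; ANCOVA would be a cheap improvement of unknown size

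*Combined protocol and SAP*

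**What the plan says.** Under Participants And Experimental Design, all 16 people took the exergaming test before allocation. Then: "Participants were matched and divided into two groups, the enzyme group, and the placebo group, based on their blood lactate levels during HIEE". The section adds: "Each group comprised 8 individuals". It does not say whether matching was by pairs, by larger sets or by balancing group means, whether assignment was random, or which lactate reading was used.

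Under Statistical Analysis, a group × time mixed ANOVA "was used to compare the variables of lactate, heart rate and training impulse between two groups before and after the 14-days of supplementation". No covariate and no pair or block term appears anywhere in the document.

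Under Blood Lactate Test, each test yields five readings: "before exercise, after the fourth and eighth bouts of exercise, and at 5 and 10 minutes after exercise". The plan does not say which of them is analysed, or whether the time factor means the two tests or also the readings within a test.

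Lactate belongs to the main objective: "The primary aim of this feasibility study is to examine the effects of fruit and vegetable enzyme supplementation on aerobic capacity and blood lactate response". No target effect, SD, correlation or power is given. The only effect sizes are conventional labels, "where the ESs of 0.2, 0.5, and 0.8 are considered small, medium, and large, respectively".

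**The concern.** If time has two levels, the group × time test is a two-sample t-test on change. The pre-test value is used, but with its slope fixed at 1 instead of estimated.

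Matching makes this matter more. It brings the groups' pre-test means close together, so chance baseline differences add little to the true variability of the group contrast. The residual variance of the change scores still contains the full pre-test spread. The standard error is then too large, and the test is conservative unless the true post-on-pre slope is near 1.

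At stake is sensitivity on a primary-aim outcome with 8 people per group: a real lactate effect is more likely to be missed, and the matching buys almost nothing in the analysis. The error is not towards false positives.

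**Working it through.** **From the document:** 16 people, 8 per group; matching on exercise lactate; group × time ANOVA; significance at 0.05 (taken as two-sided).

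**Assumed, because the document does not say:** time = pre/post; 8 pairs ranked on pre-test lactate with random assignment within pair; analysed reading = matched reading; normal data; no dropout; ρ from 0.3 to 0.9; post/pre SD ratio k of 0.8, 1.0 or 1.3; effect of 0.8 post-test SD (the plan's label for large, not a design target). The plan has no power figure to reproduce.

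**Formula.** Let s1 and s2 be the pre-test and post-test SDs, with n = 8 per group.

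- Variance used by the planned test: (2/n)(s1² + s2² − 2ρ·s1·s2).
- True variance under ideal matching: (2/n)·s2²(1 − ρ²).
- Difference: (2/n)(s1 − ρ·s2)², which is never negative and is zero when the slope ρ·s2/s1 equals 1.
- SE inflation: √[(1 + k² − 2ρk) / (k²(1 − ρ²))].

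Examples: k = 1, ρ = 0.5 gives √(1/0.75) = 1.15. For k = 1.3, ρ = 0.7, the slope is 0.91 and the result is √(0.87/0.8619) = 1.00.

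**Simulation, 100,000 trials per setting.** Planned test: 14 df. ANCOVA: 13 df. The last column is the ANCOVA power gain in points, with pairs and with no matching.

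| k | ρ | SE inflation (formula) | Type I error, planned (%) | Power, planned v ANCOVA (%) | Gain, pairs v unmatched |
|---|---|---|---|---|---|
| 0.8 | 0.3 | 1.41 | 1.1 | 13 v 34 | 21 v 13 |
| 0.8 | 0.5 | 1.32 | 1.3 | 20 v 40 | 20 v 12 |
| 0.8 | 0.7 | 1.26 | 1.8 | 35 v 55 | 20 v 14 |
| 0.8 | 0.8 | 1.25 | 1.9 | 51 v 69 | 19 v 15 |
| 0.8 | 0.9 | 1.28 | 1.6 | 79 v 92 | 13 v 14 |
| 1.0 | 0.3 | 1.24 | 1.9 | 20 v 34 | 14 v 8 |
| 1.0 | 0.5 | 1.15 | 2.8 | 29 v 40 | 11 v 6 |
| 1.0 | 0.7 | 1.08 | 3.6 | 48 v 54 | 6 v 3 |
| 1.0 | 0.8 | 1.05 | 4.1 | 66 v 69 | 3.5 v 1 |
| 1.0 | 0.9 | 1.03 | 4.5 | 92 v 92 | 0.5 v −1 |
| 1.3 | 0.3 | 1.11 | 3.2 | 27 v 34 | 7 v 4 |
| 1.3 | 0.5 | 1.05 | 4.1 | 37 v 40 | 3 v 0 |
| 1.3 | 0.7 | 1.00 | 4.9 | 55 v 54 | 0 v −3 |
| 1.3 | 0.8 | 1.00 | 5.0 | 70 v 69 | −1 v −4 |
| 1.3 | 0.9 | 1.04 | 4.2 | 91 v 92 | 1 v 0 |

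ANCOVA holds its type I error at about 5% here. Without matching, the planned test has type I error of 4.9–5.1%, so the lowered error rate comes only from ignoring the matching. With equal SDs, about half of the power gap at ρ 0.3–0.7 is the ordinary advantage of ANCOVA over change scores. Analysed as planned, matching adds no power: 20% matched against 24% unmatched at ρ = 0.3, and 48% against 49% at 0.7. Under ANCOVA it adds about 2–3 points. Matching in sets of 4 gives similar type I error.

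**If another lactate reading is analysed.** The plan separates stages, "Blood lactate levels, heart rate, and ratings of perceived exertion were recorded before, during, and after exercise", and matches on levels during the exercise. On that wording only the readings after bouts 4 and 8 can be the matched one. For another reading whose post-test depends only on its own pre-test, planned type I error with equal SDs is 3.5–4.7% at a baseline correlation of 0.7 with the matched reading, and 4.3–4.8% at 0.4. If all readings share one person-level value, the planned test is correctly sized (4.9–5.1%), own-baseline ANCOVA is slightly conservative (4.1–4.7%), and adding the matching lactate as a second covariate restores about 5%.

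**Heart rate and training impulse**, if uncorrelated with the matching lactate: planned type I error is 4.8–5.2%. ANCOVA changes power by +8, +6, +3, +1 and −1 points across ρ with equal SDs, by +12 to +15 at k = 0.8, and by +4 to −4 at k = 1.3.

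**The case against.** The strongest reply is that group × time ANOVA is a recognised pre/post analysis that already uses the pre-test value, that it errs on the safe side, and that the size of any loss rests on facts the document does not give. All of that stands. Three further points also stand:

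- Even with every condition met, there is no loss when the slope is near 1 (k = 1.3, ρ 0.7–0.8).
- If the analysed reading is not the matched one, own-baseline ANCOVA can itself be the slightly conservative test, and the remedy becomes two covariates on 16 people.
- With equal SDs, ANCOVA power at 0.8 SD is still only about 34–54% at ρ 0.3–0.7, so a null lactate result stays hard to interpret.

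These points limit the claim to an efficiency and calibration improvement of unknown size, but they do not remove it. The largest loss found from own-baseline ANCOVA is about 4 points of power; the largest gain is about 21. The ambiguities about time, the matched reading and assignment need resolving whichever analysis is used.

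**Conclusion.** The concern holds. The document matches on pre-test exercise lactate and then analyses lactate with a model that neither reflects the matching nor estimates the pre-test slope.

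Under the three conditions (pre/post time factor, random assignment within matched sets, analysed reading = matched reading), the planned test is conservative unless the post-on-pre slope is near 1. Over the assumed range its type I error is 1.1–5.0%, and ANCOVA changes power by between +21 and −1 points.

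If time includes the within-session readings, or assignment was not random, these figures do not apply and nothing follows about the direction of error. The point merits a change to the plan, but it does not invalidate the planned test. Confidence is medium, because the document settles none of the three conditions.

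**What to change.** 1. Make the main between-group test for each outcome an ANCOVA: post-test value on group and that outcome's own pre-test value. Report the adjusted difference with its 95% CI.
2. For lactate, name the reading or summary used for matching and the one analysed. If they differ, add the matching lactate as a second covariate.
3. State what time means in the group × time ANOVA, and how people were assigned within matched sets. If assignment was not random, say so and report a non-randomised comparison; ANCOVA does not remove selection bias.
4. If post-test data have already been examined, label the ANCOVA post hoc.

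**Cost.** No new data are needed. Error df fall from 14 to 13, or to 12 with the second covariate. For outcomes unrelated to the matching, ANCOVA loses about 1 point of power at ρ = 0.9 with equal SDs, and up to about 3–4 points where the slope is close to 1. The second covariate costs about 1–3.5 points if the matching lactate adds nothing, and gains about 1–6 points if the readings share a person-level value.

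### The plan does not say how the five lactate samples and repeated heart-rate readings per test enter its pre/post ANOVA, and it has no primary lactate variable or multiplicity rule

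*Combined protocol and SAP*

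**What the plan says.** The inferential plan is one sentence in Statistical Analysis: a mixed two-way ANOVA, group by time, "was used to compare the variables of lactate, heart rate and training impulse between two groups before and after the 14-days of supplementation". The threshold follows: "Statistical significance was set as $p < 0.05".

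The measurement sections describe more than one value per test:

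- Blood Lactate Test: "The blood lactate was measured at five time points: before exercise, after the fourth and eighth bouts of exercise", plus samples 5 and 10 minutes after exercise.
- Training Impulse: heart rate and RPE are taken "At the end of each exercise bout (8 bouts in total) and during the recovery period before the next bout (7 bouts in total". That is 8 + 7 = 15 readings, although the same paragraph says the process was repeated 8 times, so the count is not certain.
- % HRmax Calculation Method: "HR was recorded every 5 seconds using a heart rate monitor". This trace has a stated use, which is to obtain % HRmax for the zone-weighted training impulse.
- Each of the two training-impulse scores is a sum over the test, so each already gives one value per test.

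The Introduction sets the aim as the "effects of fruit and vegetable enzyme supplementation on aerobic capacity and blood lactate response" and gives a mechanism: "These enzymes are known to facilitate faster clearance of lactate from the bloodstream, thereby enhancing recovery and reducing fatigue". Participants And Experimental Design adds: "Participants were matched and divided into two groups, the enzyme group, and the placebo group, based on their blood lactate levels during HIEE". It does not say which lactate value was used for matching or how members of a match were assigned.

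**The concern.** A two-way model has one time factor. Lactate and heart rate have two: visit (pre-test or post-test) and sampling point within the test. The before-and-after wording suggests that time means visit. The plan then needs either one value per visit or a separate model for each sampling point, and it says neither. No peak, mean, area under the curve or clearance measure is defined.

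Two things are at stake. First, the lactate result to report can be chosen after the data are seen, and one p < 0.05 among five sampling times could be read as a supplement effect. Second, with 8 people per group the choice of summary largely decides what effect can be detected, and what a positive result would mean. Faster clearance and lower production during exercise are different claims and need different summaries.

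**Working it through.** **Inputs from the documents.** 16 participants, 8 per group; five lactate samples per test; threshold 0.05 (taken as two-sided). The plan states no SD, correlation, target effect or power, so it has no figure to reproduce.

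**Assumed inputs.** Lactate SDs 0.3, 1.5, 2.0, 2.2 and 2.0 mM at the five times; within-test AR(1) correlation 0.6, 0.8 or 0.9 between neighbouring samples; pre-post correlation ρ of 0.4, 0.6 or 0.8. Where matching is modelled, people are ranked on a pre-test lactate value, paired, and randomised within pairs. Four matching values were tried: the four-sample mean, the sample after bout 4, the sample after bout 8, and the 5- and 10-minute mean. The four samples are those taken after bouts 4 and 8 and at 5 and 10 minutes. Each cell has 20,000 simulated trials.

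**1. False positives if each lactate time is tested separately.** For k independent tests the chance of at least one false positive is 1 − 0.95^k: 22.6% for k = 5 and 18.5% for k = 4. The samples are correlated, which lowers these:

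| Tests | No matching | Matched |
|---|---|---|
| Five times | 11.9–19.6% | 7.7–18.4% |
| Four times, pre-exercise sample omitted | about 11–16% | about 6–15% |

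A separate calculation with equal correlation among the five change scores gives 21.2%, 18.9%, 15.5% and 10.7% at 0.3, 0.5, 0.7 and 0.9.

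**2. The planned ANOVA on one summary.** With two visits, the group-by-time term is a t-test on change (14 df). Its variance is proportional to 2(1 − ρ). Adjusting the post-test value for the pre-test value (ANCOVA, 13 df) gives 1 − ρ². The ratio is (1 − ρ²) / [2(1 − ρ)] = (1 + ρ)/2, that is 0.70, 0.80 and 0.90 at ρ = 0.4, 0.6 and 0.8.

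Simulated power for a 1 SD effect on the 5- and 10-minute mean (within-test correlation 0.8; matching on the four-sample mean):

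| ρ | Matched: ANCOVA v 2×2 | Gap | No matching: ANCOVA v 2×2 | Gap |
|---|---|---|---|---|
| 0.4 | 52.0% v 37.8% | 14.2 | 50.1% v 39.9% | 10.2 |
| 0.6 | 63.7% v 55.2% | 8.5 | 61.2% v 55.6% | 5.6 |
| 0.8 | 86.2% v 84.3% | 1.9 | 84.6% v 83.6% | 1.0 |

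Most of the gap is present without matching, so it comes mainly from analysing change scores.

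Type I error of the 2×2 on one lactate level (four-sample mean or recovery mean) is 4.8–5.3% without matching and 2.1–4.2% when matched on that same level. ANCOVA stays at 4.6–5.4%. The matched figures depend on random allocation within pairs.

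**3. Which summary.** ANCOVA rejection rates at ρ = 0.6, within-test correlation 0.8, matched on the four-sample mean:

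| True effect | Fall, bout 8 to 10 min | 5/10-min mean | Four-sample mean |
|---|---|---|---|
| 1 SD at 5 and 10 min only | 75% | 68% | 30% |
| Overall shift proportional to SD | about 5% | 57% | 64% |
| Overall shift, equal mM | about 5% | about 50% | 64% |

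The fall does not react to an overall shift because both of its samples move equally: by definition for an equal-mM shift, and because both assumed SDs are 2.0 mM for the proportional one. The 5/10-minute mean is a level: it reacts to faster clearance and to lower production alike. At within-test correlation 0.6 the ranking for a recovery-only effect reverses: fall 51%, recovery mean 73%.

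**The case against.** The strongest reply is that this is called a feasibility study, that a pre/post ANOVA on one summary is sound, and that five separate lactate tests are only one reading. All of that stands. It lowers the stakes, but the stated primary aim is still a supplement effect and the plan still tests it at 0.05. Under either reading the plan must say what the lactate variable is.

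Baseline adjustment could also be called a preference. At a pre-post correlation of 0.8 that is nearly true, since the gain is about 1–3 points over the matching rules tried. At 0.4 and 0.6 it is material.

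Several stronger readings are tempting but not supported:

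- That the planned ANOVA is invalid. It is not, given one value per visit.
- That the plan commits to five tests and so carries a known inflated error rate. It neither states nor excludes this.
- That ignoring the matching is the main cause of lost power. The gap is mostly there without matching. The extra conservatism needs random allocation within pairs, and the protocol says only that people were matched and divided.
- That the 5-second heart-rate trace is a further unassigned outcome. It feeds % HRmax and the training impulse. The open question is only which reading or summary is the heart-rate variable.

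**Conclusion.** The gap is real and needs no assumption to establish: the plan does not define how within-test lactate and heart-rate samples enter the model, which lactate variable is primary, or how multiple tests are handled. It should be corrected.

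Its size does rest on assumptions. If every lactate time is tested, the false-positive chance is about 8–20%, or about 6–16% without the pre-exercise sample. On one summary the 2×2 holds its error rate, or is conservative at about 2–4% if allocation was random within pairs matched on that lactate level. It gives up about 14, 9 and 2 points of power to ANCOVA at pre-post correlations 0.4, 0.6 and 0.8 in the matched case above.

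A reader might infer that the 5/10-minute mean is the natural clearance measure because it is taken in recovery. The documents do not support that: it is a recovery level and cannot separate clearance from lower production. Nor does the correction make 16 people sufficient. By noncentral t, ANCOVA power for a standardised difference of 0.8 is 40% at an assumed pre-post correlation of 0.5 and 69% at 0.8.

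**What to change.** In Statistical Analysis:

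1. State that time means pre-test v post-test.
2. Name one lactate summary per test as the primary lactate result, taken from the hypothesis. Use the fall from after bout 8 to 10 minutes if faster clearance is meant. Use the mean of the four exercise and recovery samples, or the area under the curve, if overall response is meant.
3. Test it once at 0.05 as the post-test group difference adjusted for the pre-test value of the same summary, with a 95% CI. A 2×2 on that summary is a valid, less efficient fallback.
4. Name one heart-rate summary per test from the bout and recovery readings.
5. Label individual lactate times, heart rate and both training-impulse scores exploratory, or Holm-adjust them.
6. The methods are written in the past tense. If the data have already been seen, label the choice of summary post hoc.

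If the fall is chosen, report its two component samples as well, because a change confined to the end-of-exercise sample also alters it.

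The cost is wording and one derived variable per measure, with no new data. Single-time differences can no longer be claimed as confirmatory. ANCOVA spends one degree of freedom (13 v 14) and assumes a common slope that 16 people can check only roughly. A poorly chosen summary loses power. Under an overall shift, the recovery mean costs about 6–7 points if the shift is proportional to SD and about 13–14 if it is equal in mM, and the fall has no power under either. The fall also has less power than the recovery mean when within-test correlation is low.

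This does not settle aerobic capacity, which the aim names but which has no variable in the ANOVA.
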